2. STUDY PROCEDURES

2.1 Study Procedures Overview

After informed consent is received, a neurological examination will be performed and multiple screening assessments will be conducted including a tDCS and MRI safety screening (see below). If the patient passes the initial screening portion, speech and language diagnostic testing will be conducted during the same visit (Visit 1). During the next two visits (Visits 2 and 3), patients will undergo baseline assessments of naming ability and connected speech, and structural and functional MRI examinations. The fourth visit will include collection of blood sample, electrode positioning and tDCS treatment administration. Patients will receive 15 sessions (Visits 4-18) of tDCS treatment administration. At the beginning of Visit 4, eligible patients will be randomized to receive either A-tDCS (1 mA) or S-tDCS (placebo) for 15 consecutive weekdays (20-min per each 45-min behavioral treatment session). A computerized anomia treatment will be coupled with the stimulation. The computerized treatment task will be 45-minutes in total length, so that it will commence at the same time as the tDCS administration and continue for another 25-minutes after the tDCS has ceased. To assess cardiovascular arousal, blood pressure and heart rate will be measured before and after each session. Additionally, discomfort ratings will be recorded following the end of each session using the *Wong-Baker FACES Pain Rating Scale* and a weekly neurological exam will be administered by a neurologist. Utilizing a computerized picture naming assessment (which combines the 175 items from the PNT and 80 treated items) of trained and untrained nouns, all patients will be assessed at 8 different time points throughout the experiment: twice at baseline (Visit 2 and 3), twice immediately following the fifteenth (and final) treatment session (Visit 19 and Visit 20), twice at 4 weeks follow-up (Visit 21 and Visit 22), and twice at 6 months follow-up (Visit 23 and Visit 24).

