3.5.2 Post-Testing Phase

The longer follow-up post-testing phase will provide exploratory information on whether the immediate post-testing improvement after 3 weeks of treatment can be sustained. The mean (95% CI) changes from baseline to immediate (within 1 week) post-testing, 4 weeks post-testing and 6 months post-testing will be reported. Box and whisker plots will be produced to show the distribution of naming accuracy over time by treatment group. To explore the longitudinal data, a general linear mixed model (GLMM) will be constructed by tDCS group for the dependent variable (anomia). The GLMM will incorporate random subject effects to account for repeated measurements being made on subjects; the model will include time, aphasia type, severity, and clinical center as independent variables. A similar modeling approach may be applied to other secondary outcomes.

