9.2 Exploratory Analyses of the Primary Outcome measures

Spearman's correlation coefficients will be computed for pre-post change in anomia versus aphasia type first using all patients and then by tDCS group. This association will be further explored using the longitudinal data in a GLMM model described in section 3.14 (post-testing phase). Since there will be little statistical power to detect an interaction of aphasia type and treatment, we will examine the main effect of aphasia type (adjusting for the other covariates) by tDCS group.

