9.3 Post-Testing Phase

The longer follow-up post-testing phase will provide exploratory information on whether the immediate post-testing improvement after 3 weeks of treatment can be sustained. The mean (95% CI) changes from baseline to immediate (within 1 week) post-testing, 4 weeks post-testing and 6 months post-testing will be reported. Box and whisker plots will be produced to show the distribution of naming accuracy over time by group.

To explore the longitudinal data, a Repeated Measures model (SAS® MIXED procedure with REPEATED sub-command) will be constructed by tDCS group. The model will include the following fixed effects: visit (as a classification variable), aphasia type, severity, and clinical center as independent variables. Various error structures will be examined (e.g., compound symmetry, autoregressive, unstructured), and the final structure will be selected based on the model Akaike Information Criteria. A similar modeling approach may be applied to other secondary outcomes (e.g., number of naming errors).

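### SAP 9.2 asks how aphasia type relates to pre-post change in naming, but reads the answer from a type main effect in a longitudinal model with no type-by-visit term, and the SAP does not state that model's response

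*SAP*

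**What the plan says.** SAP 9.2 (Exploratory Analyses of the Primary Outcome measures) fixes the question in its first sentence: "Spearman's correlation coefficients will be computed for pre-post change in anomia versus aphasia type", over all patients and then by arm. It continues: "This association will be further explored using the longitudinal data in a GLMM model". The section number it gives for that model, 3.14, does not exist in the SAP; the matching section is 9.3. SAP 9.2 sets aside the interaction of type with treatment for lack of power and says instead that "we will examine the main effect of aphasia type (adjusting for the other covariates) by tDCS group".

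SAP 9.3 (Post-Testing Phase) specifies a repeated measures model fitted separately in each tDCS group: "The model will include the following fixed effects: visit (as a classification variable), aphasia type, severity, and clinical center as independent variables". The error structure is to be chosen by AIC, with compound symmetry, autoregressive and unstructured as examples. The section does not name the response, and it does not say whether baseline visits enter as responses.

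Protocol 3.5.2 does name a response: "a general linear mixed model (GLMM) will be constructed by tDCS group for the dependent variable (anomia"). It uses random subject effects and says that "the model will include time, aphasia type, severity, and clinical center as independent variables".

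Protocol 2.1 schedules eight naming assessments: two each at baseline, immediately after treatment, at 4 weeks and at 6 months. Neither document adds a type-by-visit term or a baseline naming covariate.

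**The concern.** The question is about change; the term chosen to answer it is a main effect. In a model whose only terms are visit, type, severity and center, every aphasia type is given the same time course. The type coefficient then says how far apart the types sit, not how differently they move.

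Types may well differ in naming before treatment. Such a difference could be read as a difference in response when all types gain equally. A true difference in gain could be diluted, cancelled or reversed by where the types started. This arises inside a single arm, so it is separate from whether the arms are compared. At stake is an exploratory statement about which patients improve, in a trial meant to inform a decision on Phase III.

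**Working it through.** The documents give no figure for this analysis, so there is none to reproduce. The check is of what the term estimates, followed by an illustration of size.

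**1. Level as response, baseline visits included.** Add a constant c to every score of one aphasia type at every visit. No patient's gain changes, yet the fitted type coefficient moves by exactly c. This holds for any error structure, with or without missing visits, and with severity and center in the model.

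Equivalently, with complete data the generalised least squares type effect weights the type difference at each visit by w = Σ⁻¹1 / (1′Σ⁻¹1), and these weights sum to 1. A change contrast has weights that sum to 0. With the four assessment periods (each pair averaged), the weights are:

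| Error structure | Baseline | Immediate post | 4 weeks | 6 months |
|---|---|---|---|---|
| Compound symmetry | 0.25 | 0.25 | 0.25 | 0.25 |
| AR(1), correlation 0.9 (assumed) | 0.455 | 0.045 | 0.045 | 0.455 |
| Unstructured (one assumed example) | 0.489 | 0.164 | 0.158 | 0.189 |

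The average has equal weights under compound symmetry with complete data, not in general. None of these structures produces a change contrast.

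**2. What a 3-item difference in gain becomes.** Suppose it is present at all three later periods.
- Equal starting levels, compound symmetry: 0.75 × 3 = 2.25.
- Equal starting levels, AR(1): (1 − 0.455) × 3 ≈ 1.6.
- Better-gaining type starts 2.25 items lower, compound symmetry: −2.25 + 2.25 = 0.
- Better-gaining type starts 10 items lower, compound symmetry: −10 + 2.25 = −7.75, the wrong sign.

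**3. Size in one arm.**
- From the SAP: 37 patients per arm (section 4) and SD 2.6 (section 8.3), used here as the SD of change.
- Assumed: two types split 18/19, between-patient SD of level after adjustment 10, 20 or 30 items, compound symmetry, complete data, two-sided 5% tests.

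The SD of a patient's mean over the four periods is √(SD_between² + (2.6²/2)/4). For SD_between = 10 this is √(100 + 0.845) = 10.04. The standard error of the type effect is 10.04 × √(1/18 + 1/19) = 3.30. For the change contrast it is 2.6 × √(1/18 + 1/19) = 0.855. Rejection rates from the noncentral t distribution with 35 df:

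| Truth | Test | SD 10 | SD 20 | SD 30 |
|---|---|---|---|---|
| Equal gains, 10-item level gap | Type main effect | 84% | 31% | 17% |
| Equal gains, 20-item level gap | Type main effect | 100% | 84% | 50% |
| 3-item gain difference, no gap | Type main effect | 10% | 6% | 6% |
| Equal gains, any gap | Change contrast | 5% | 5% | 5% |
| 3-item gain difference, any gap | Change contrast | 93% | 93% | 93% |

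Simulation (4,000 runs per scenario) agrees: with a 30-item gap and equal gains the change contrast rejected in about 5% of runs, and with a 3-item gain difference in 92% to 93%.

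The 93% depends on the even split. For the same difference and SD it is 80% at 8/29 and 56% at 4/33.

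**4. Change from baseline as response.** The type effect is then a difference in change, averaged over immediate, 4-week and 6-month testing. A 3-item difference confined to immediate post-testing would appear, with equal weights, as (3 + 0 + 0)/3 = 1.

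**The case against.** The strongest reply is that the SAP never says the response is naming level. A change response is a fair reading: SAP 9.2 is headed as an analysis of the primary outcome, which is a change; the association it names is with pre-post change; and SAP 9.3 reports changes from baseline at three later times. Under that reading the main effect does concern change, and averaging over follow-up is a reasonable longitudinal target. This stands in part. A reader might infer that the planned model cannot address the question at all, and the documents do not support that. What they do establish is that the SAP leaves the response open, the protocol's wording points to level, and neither reading isolates the pre-post contrast.

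Also valid:
- **Severity adjustment.** AQ and aphasia type both come from the WAB-R, which includes naming, so adjustment may shrink the level gap. It does not change what the term estimates.
- **Inputs.** The documents give no level gap, between-patient SD or number of types. The rates above are not error rates of this trial.
- **Status.** The analysis is exploratory, and the Spearman step in SAP 9.2 already uses the change score.

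The low-power argument in SAP 9.2 does not answer the point. It concerns type by treatment, whereas type by visit is a within-patient comparison inside one arm.

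**Conclusion.** The point holds in a limited form. With naming level as response and baseline visits included, the type main effect is a weighted level difference under any error structure. It can be large when gains are equal and close to zero when they differ. With change as response, it answers the pre-post question only in part. That conclusion follows from the model terms as written and needs no numerical assumption beyond the choice of response.

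The size does rest on assumptions. For a 10-item gap with equal gains, false signals run from 17% to 84%. For a 3-item gain difference, power is 6% to 10% with the main effect against 93% with the change contrast. All of these assume two evenly split types, between-patient SD 10 to 30, compound symmetry and complete data.

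Two stronger readings should be resisted. The primary futility test does not use this model, so the go/no-go decision is unaffected. Nor do the documents say that level differences will be reported as differences in response; they say only that the main effect will be examined. The wording should be put right because it leads to that misreading.

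**What to change.** - **SAP 9.3 and Protocol 3.5.2:** name the response and say whether baseline visits are among the responses. Add aphasia type by visit alongside the existing main effects. Use the four assessment periods as visit levels and group rare types.
- **SAP 9.2:** in place of the type main effect, report the between-type contrast in change from baseline (mean of Visits 2 and 3) to immediate post-testing (mean of Visits 19 and 20), with a 95% CI, by tDCS group. Correct the cross-reference from 3.14 to 9.3.

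SAP section 2 already foresees an update before database lock, so this is wording and one model term. The cost in degrees of freedom is (4 − 1) × (types − 1): 3 for two types and 9 for four, against 7 and 21 if all eight sessions are separate levels. Precision will be low if the types are unevenly split, as the 56% at 4/33 shows, so the interval should carry more weight than the p-value.

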9.3 Post-Testing Phase

The longer follow-up post-testing phase will provide exploratory information on whether the immediate post-testing improvement after 3 weeks of treatment can be sustained. The mean (95% CI) changes from baseline to immediate (within 1 week) post-testing, 4 weeks post-testing and 6 months post-testing will be reported. Box and whisker plots will be produced to show the distribution of naming accuracy over time by group.

To explore the longitudinal data, a Repeated Measures model (SAS® MIXED procedure with REPEATED sub-command) will be constructed by tDCS group. The model will include the following fixed effects: visit (as a classification variable), aphasia type, severity, and clinical center as independent variables. Various error structures will be examined (e.g., compound symmetry, autoregressive, unstructured), and the final structure will be selected based on the model Akaike Information Criteria. A similar modeling approach may be applied to other secondary outcomes (e.g., number of naming errors).

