2. STATISTICAL ANALYSIS PLAN AND STATISTICAL REPORTS

This document provides the details of the statistical analyses planned for the trial. Prior to locking the database and breaking the code, this Statistical Analysis Plan (SAP) will be updated. The SAP will define all “pre-specified, pre-planned analyses.”

The DCU Biostatistics Core under the direction of [name] will generate closed and open DSMB reports semi-annually or more frequently, as determined by the DSMB. Each DSMB report provides cumulative summary statistics on enrollment; subject status in the study (e.g., number completed study, drop outs, etc); baseline characteristics; safety data, including AEs and SAEs by MEDdra code, severity, and relatedness to the study intervention; and data management/quality information (e.g., timeliness and completeness of data entry by the clinical centers via the WebDCU™; number of data queries generated and resolved). The statistics for the closed DSMB Reports are provided by intervention group displayed as A or B. The open report contains aggregated statistics only, i.e., not by intervention group.

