8.3 Sample Size Determination

In preliminary studies, the mean difference in change from baseline in the active and sham groups in naming accuracy was ~2.5 points (Baker, Rorden, & Fridriksson, 2010, Fridriksson et al., submitted). In one study, the S-tDCS (sham) group improved ~1.2 point from baseline to 1 week (Baker, Rorden, &

Fridriksson, 2010). In another study, the S-tDCS group improved ~3.9 points from baseline to 1 week (Fridriksson et al., submitted). For power calculations, we assumed the mean change from baseline to immediate (1 week) post-testing for the A-tDCS group under the null hypothesis of non-futility is equal to $\mu_s + \delta = 4 + 1.5 = 5.5$. When the sample size is 33 per group, a two sample t-test with a 0.10 one-sided significance level will have 85% power to reject the null hypothesis that the A-tDCS treatment is 1.5 points better than S-tDCS (sham) and declare futility when the A-tDCS treatment comes from a distribution with mean change of 4 (assuming the pooled SD is 2.6). As with most clinical studies, a certain amount of drop-outs (including subject withdrawal or lost-to-follow-up) can be expected. In preliminary studies less than 5% of visits were missing. Conservatively assuming the drop-out rate to be no more than 5% over 5 weeks, the required sample size was inflated from 33 to 37 per intervention arm to account for the effect of the drop-outs in the intent-to-treat analysis using an inflation factor (Friedman, et al, 1985).

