9. SECONDARY ANALYSES

9.1 Secondary Efficacy Outcome measures

In addition to the primary outcome, several secondary analyses will be conducted. We will examine changes in types of naming errors (defined by the PNT) by tDCS treatment group. The Cinderella story will be analyzed by comparing lexical diversity (VOCD) for nouns, verbs and adjectives; number and types of errors; length and patterns of pauses by treatment group. Pre and post comparisons with both non-aphasic and aphasic speakers from the AphasiaBank database who share a number of demographic features (e.g., type and severity of aphasia, age, etc) will also be made.

At the end of the study, for the interval scale variables, mean change from baseline to immediate post-testing in secondary outcome measures will be reported by treatment group along with the 95%

confidence intervals. Treatment comparisons will be made with a paired *t*-test. For binary variables, the proportion of subjects immediately post-testing will be reported by treatment group along with the 95% confidence intervals.

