9.4 Exploratory Analyses of BDNF polymorphism

A two group *t*-test with a 0.05 two-sided significance level will have 80% power to detect a difference in mean reaction time of 2.6, assuming that the common standard deviation is 2.6, when the sample sizes in the two allele groups are 12 having at least 1 MET allele and 25 without the MET allele, respectively (a total sample size of 37 patients in the A-tDCS group assuming 33% have at least 1 MET allele).

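### The exploratory follow-up naming model lists no treatment or treatment-by-visit effect, and no between-arm naming contrast is specified at 4 weeks or 6 months

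*SAP*

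**What the plan says.** SAP 9.3 describes the follow-up phase as exploratory and asks whether the gain seen right after treatment lasts. It plans three outputs:

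- mean changes from baseline with 95% CIs at immediate, 4-week and 6-month post-testing;
- box plots of naming accuracy over time by group;
- a repeated-measures model built by tDCS group, of which it says: "The model will include the following fixed effects: visit (as a classification variable), aphasia type, severity, and clinical center". The error structure is chosen by AIC.

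Protocol 3.5.2 has the same outputs and a mixed model with random subject effects, also built by tDCS group: "the model will include time, aphasia type, severity, and clinical center as independent variables".

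SAP 9.2 refers to the longitudinal model of the post-testing phase. Because power for a type-by-treatment interaction is low, it says "we will examine the main effect of aphasia type (adjusting for the other covariates) by tDCS group".

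In SAP 9.1, the paragraph that sets out reporting and treatment comparisons is tied to one time point: "mean change from baseline to immediate post-testing in secondary outcome measures will be reported by treatment group".

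Naming is measured in all patients at the later times. Protocol 2.1 schedules it "twice at 4 weeks follow-up (Visit 21 and Visit 22), and twice at 6 months follow-up (Visit 23 and Visit 24".

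**The concern.** The trial compares tDCS with sham, and both arms receive the same computerized anomia treatment. Improvement in the sham arm is therefore expected. SAP 8.3 reports that in one preliminary study "the S-tDCS group improved ~3.9 points from baseline to 1 week", and it assumes a sham change of 4 items for the power calculation. A gain that lasts to 6 months in the A-tDCS arm may be a lasting effect of training alone. Only a comparison with sham at the same time point separates the two, and the plan does not specify one for naming.

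If futility is not declared, the sponsor would consider a Phase III study (SAP 8.2), and whether any advantage over sham persists would be useful to know then. If the contrast is not fixed in advance, its form, adjustment and error structure would be chosen after unblinding. The alternative would be to set two within-arm results side by side, which is a poor substitute for a contrast.

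**Working it through.** **1. Search for the contrast.** The places where a between-arm naming comparison at 4 weeks or 6 months could appear are these:

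| Place | Time points | Between-arm difference specified? |
|---|---|---|
| SAP 8.1–8.3, Protocol 3.4 | immediate | yes (primary futility test) |
| SAP 9.1, Protocol 3.5.1, reporting paragraph | immediate | yes, for secondary outcomes |
| SAP 9.3, Protocol 3.5.2, mean changes and box plots | immediate, 4 weeks, 6 months | no, descriptive only |
| SAP 9.3, Protocol 3.5.2, model | all visits | no, treatment is not a listed effect |

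**2. The possible readings of the model.** The most natural is a separate model per arm. Each model then estimates change over visits within one arm and contains no contrast. If a single joint model was meant, treatment is still not among the listed effects, so the list as written yields no treatment estimate. The gap exists on either reading.

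**3. The plan's own figure.** SAP 8.3 gives 33 per group for one-sided alpha 0.10, 85% power, difference 1.5 and SD 2.6.

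n = 2 × (1.2816 + 1.0364)² × 2.6² / 1.5² = 2 × 5.373 × 6.76 / 2.25 = 32.3, rounded up to 33.

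Power at 33 per group is 85.2% by the noncentral t. The figure reproduces and is not in question. No corresponding figure is given for follow-up.

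**4. Precision of the missing contrast.** The 95% half-width of an unadjusted difference in mean change is t(0.975, 2n − 2) × SD × √(2/n). The n of 37 per arm is from SAP 4. The SD of 2.6 is from SAP 8.3 and applies to immediate post-testing. The documents give no SD and no dropout rate for 6 months, so every SD below is an assumption at follow-up. For example, at n = 37 and SD 2.6: SE = 2.6 × √(2/37) = 0.604, and 1.99 × 0.604 = 1.21.

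| Assumed SD | Half-width, 37 per arm | Half-width, 33 per arm |
|---|---|---|
| 2.6 | 1.21 | 1.28 |
| 3.9 | 1.81 | 1.92 |
| 5.2 | 2.41 | 2.56 |
| 10 | 4.64 | 4.92 |

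Any gain in precision from adjusting for baseline is not counted.

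**5. Why two within-arm results do not replace a contrast.** Suppose both arms have the same true change, with 37 per arm and SD 2.6, and each arm is tested separately against zero change at two-sided 0.05. If p is the chance that one arm is significant, the arms disagree with probability 2p(1 − p).

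| Assumed true change in both arms | p | Chance of disagreement |
|---|---|---|
| 0.5 | 0.206 | 0.33 |
| 0.8 | 0.445 | 0.49 |
| 1.2 | 0.780 | 0.34 |
| 4 | about 1 | about 0 |

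The risk of a false impression is therefore real if gains fade, and negligible if both arms keep a gain near 4 items. The later changes and SD are assumptions.

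**The case against.** The strongest reply is that the plan does what it sets out to do. The phase is labelled exploratory, its stated question is whether improvement lasts, and per-arm models answer that. This stands, and it is why the point has low priority.

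A second reply concerns the wording. SAP 9.1 and SAP 10 use a similar by-group phrase for comparisons, so the phrase alone does not prove separate models. SAP 9.2 is consistent with the within-arm reading but is not firm support. It points to a GLMM in a section 3.14 that is not in the SAP, whereas SAP 9.3 describes a REPEATED-type model. Its remark on interaction power also suggests that a joint model was at least considered. This stands too. It leaves open whether the models are separate, but it does not supply the missing terms.

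A third reply is that a reader could subtract the two arms' estimates. That is possible, since the arms are independent. But the contrast, the covariate values at which it is taken and its CI would all be unspecified, and AIC could select a different error structure in each arm.

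Two stronger readings are tempting, and the documents do not support them:

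- From 4 and 5.5 in SAP 8.3, a reader might infer that 4/5.5 = 73% of the active-arm gain is expected without tDCS. But 5.5 is the non-futility boundary (sham plus the 1.5 margin), not an expected gain. In the scenario that the plan powers, both arms gain 4.
- A reader might infer that the added contrast would be informative. That depends on the follow-up SD. At an assumed SD of 3.9 or more, the half-width already exceeds the 1.5-item margin.

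**Conclusion.** The point holds as a low-priority improvement. As written, the model in SAP 9.3 and Protocol 3.5.2 yields no estimate of whether a tDCS-versus-sham difference in naming persists at 4 weeks or 6 months, although the randomized data for it will be collected. This rests on the listed effects and on the absence of a contrast elsewhere, not on one reading of the by-group phrase.

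The size of any loss cannot be stated, because precision at follow-up is unknown. The half-widths, about 1.2 to 4.6 items with 37 per arm, rest on assumed SDs of 2.6 to 10 and on complete follow-up.

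The primary futility test is untouched. The point is also limited to naming accuracy: the first paragraph of SAP 9.1 sets no time limit on the comparisons of naming-error types or the Cinderella measures, so a reader should not extend it to them.

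**What to change.** In SAP 9.3 and Protocol 3.5.2:

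- Fit one repeated-measures model to both arms, adding treatment and treatment-by-visit to the effects already listed.
- Account for baseline naming once, either as an outcome row or as a covariate, not both. With baseline as an outcome row, the estimate is the between-arm difference in change from baseline. With baseline as a covariate, it is the adjusted difference at each post-treatment visit.
- Report the A-tDCS minus S-tDCS difference with its 95% CI at immediate, 4-week and 6-month post-testing, labelled exploratory. Each time point has two visits, so if visit stays as the classification variable, the time-point difference is the mean of the two visit-specific differences.
- Keep the per-arm means and box plots as description.

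The cost is wording and a little extra analysis. No new data are needed, and the SAP already provides the occasion: "Prior to locking the database and breaking the code, this Statistical Analysis Plan (SAP) will be updated". The downside is that the exploratory estimates may be imprecise, which the CIs will show.

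### The protocol and SAP specify different longitudinal models for eight very unevenly spaced sessions; a 6-month interval taken from either model can be too narrow

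*SAP*

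**What the plan says.** Protocol 2.1 schedules the naming assessment eight times: twice each at baseline (Visits 2 and 3), after treatment (19 and 20), at 4 weeks (21 and 22) and at 6 months (23 and 24).

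The two documents model these data differently.

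- Protocol 3.5.2: "The GLMM will incorporate random subject effects to account for repeated measurements being made on subjects". It names no other covariance structure and no selection step.
- SAP 9.3: "a Repeated Measures model (SAS® MIXED procedure with REPEATED sub-command) will be constructed by tDCS group". Time enters as a categorical factor: "The model will include the following fixed effects: visit (as a classification variable), aphasia type, severity, and clinical center as independent variables". For the covariance, "Various error structures will be examined (e.g., compound symmetry, autoregressive, unstructured), and the final structure will be selected" by AIC.

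SAP 9.2 refers to a mixed model in a section 3.14 that the SAP does not contain.

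Both documents also promise, before the model is introduced, that "The mean (95% CI) changes from baseline to immediate (within 1 week) post-testing, 4 weeks post-testing and 6 months post-testing will be reported". Neither says whether these intervals come from the model or from the observed changes. Both call the phase exploratory.

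**The concern.** The post-testing phase is there to show whether the gain lasts, so the precision of the 6-month change matters. A random intercept, or compound symmetry, assumes that two sessions a day apart are no more alike than two sessions six months apart. If patients drift over time, the model pools the short-gap and long-gap differences and understates the variance of the 6-month change.

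The SAP's AIC step can escape this by choosing unstructured. However, it charges that choice 36 parameters against 2, in a fit to at most 37 patients. Separately, two different prespecified models leave it open which one is the plan.

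**Working it through.** **1. The plan's own figures.** No figure is given for the longitudinal model. The sample size in SAP 8.3 reproduces: difference 1.5, SD 2.6, one-sided 0.10 gives 33 per group with 85.2% power (noncentral t), and 33/0.95² = 36.6, so 37. From this come n = 37 per arm and the only planning SD, 2.6 for the immediate change.

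**2. Assumed inputs.** The documents give no between-session correlations or exact days. Assumed: sessions on days 0, 1, 22, 23, 50, 51, 202 and 203; session-noise SD *s*; true-change SD *d* at 6 months; between-patient SD 35 in the random-walk runs (it cancels from a change); complete data; no covariates.

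**3. Why compound symmetry is too narrow.** The 6-month change is the mean of Visits 23 and 24 minus the mean of Visits 2 and 3.

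- True variance: d² + s²/2 + s²/2 = d² + s².
- Compound symmetry uses one within-patient variance, the average over the 28 session pairs of half the variance of their difference. If drift accumulates in proportion to time, this is s² + ½ × (d²/202) × (mean gap). The 28 gaps sum to 2540 days, so the mean is 90.7.
- The contrast multiplies that variance by 4 × 0.25 = 1.

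With s = 3 and d = 4, the true variance is 9 + 16 = 25. Compound symmetry gives 9 + ½ × (16/202) × 90.7 = 12.6. The SE ratio is √(12.6/25) = 0.71, and approximate coverage is 2Φ(1.96 × 0.71) − 1 = 84%.

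**4. What AIC must overcome.** Unstructured over 8 sessions has 8 × 9/2 = 36 parameters and compound symmetry has 2. Unstructured is chosen over compound symmetry only if −2 log-likelihood falls by more than 2 × (36 − 2) = 68.

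**5. Simulated coverage of the nominal 95% interval** (one arm; REML fits of compound symmetry, AR(1) and unstructured; choice by AIC; n = 37):

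| Assumption | Compound symmetry forced | AIC rule | Unstructured |
|---|---|---|---|
| 1-day correlation 0.95-0.98, falling to 0.73-0.94 at 6 months | 76-80% | 94-96% (unstructured chosen in 93-98% of runs) | about 95% |
| Flat correlation 0.95 | – | 95% (compound symmetry chosen in over 99.9%) | – |
| Random walk, s = 3-4, d = 2.5-12 | 72-93% | 89-95% | 95-96% |
| Same, s = 3, d = 4 | about 84% (step 3) | 88-89% (compound symmetry kept in 68-75%) | – |
| Immediate-change SD held at 2.6, s = 2.0-2.4, later drift SD 2-3 | – | 89-92% (compound symmetry kept in 34-96%) | 94-96% |
| Further set with varied drift | 65-95% | 89-97% (about 89-90% under moderate drift) | 94-97% |

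With 33 patients, the row held at SD 2.6 fell to 87-91%. The lowest AIC-rule result in any set was 86%, from 600 runs with Monte Carlo error of about 1.3 points.

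**6. Why the rows differ.** In units of total variance, the first row has s² ≈ 1 − r(1 day) and d² ≈ 2 × [r(1 day) − r(6 months)]. For correlations 0.980 and 0.937, d²/s² = 0.086/0.020 = 4.3, so d/s ≈ 2.1. For 0.948 and 0.733, 0.430/0.052 = 8.3, so d/s ≈ 2.9. Drift that large is plain enough for AIC to choose unstructured. With s = 3 and d = 4, d/s is 1.3: enough to spoil compound symmetry, often too little to pay the penalty of 68.

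**7. The other two routes.** AR(1), if forced, covers 99-100%. At n = 37 AIC chose it in under 3% of runs in the widest set and at most about 8% in any. A t interval from the observed changes covers 94-96% in the first-row scenarios, because it needs no between-session model.

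**The case against.** The strongest case against has five parts.

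- **Unstructured is on the SAP's list.** It assumes neither equal correlation nor equal spacing, and visit is categorical. This stands. A reader might infer that the 6-month intervals are simply wrong, but SAP 9.3 does not commit to compound symmetry or autoregressive. Where forced compound symmetry was worst (d = 12, 68-74% in one set), AIC never chose it and the selected model covered 93-95%.
- **The reported intervals may not come from the model.** The sentence promising them is separate from the model. This also stands: the under-coverage is conditional, and the missing statement is itself a gap.
- **Random subject effects need not mean an intercept only, and SAP section 2 makes the SAP the defining text.** Both are fair. Compound symmetry is one reading of the protocol, but the protocol offers no wording that settles it.
- **The variances are assumed.** Noise SD of 3-4 alone gives an immediate change SD of 3-4, above the planned 2.6. This is a fair criticism of those scenarios. It does not remove the point, because the runs held at 2.6 also gave 89-92%.
- **The analysis is exploratory.** This stands and limits the weight of the point.

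A reader might also infer that the autoregressive option makes the interval too wide and that the data choose between too wide and too narrow. AIC selects that structure too rarely for this to matter.

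**Conclusion.** The point holds in a limited, conditional form. The documents specify different longitudinal models for the same unevenly spaced data and should be aligned whatever the variances are. If the 6-month interval is model-based, expect coverage of about 65-95% with a random intercept or compound symmetry. Under the SAP's AIC rule expect about 89% when drift is moderate, roughly 6 points short of nominal, and close to 95% when drift is strong or nearly absent.

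These sizes rest on assumed visit days and variances, complete data and no covariates. With missing sessions, the choice of structure would also affect the point estimates. Nothing here touches the primary futility test, which uses only the immediate post-treatment change.

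**What to change.** Put the same specification in Protocol 3.5.2 and SAP 9.3, and correct the cross-reference in SAP 9.2:

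1. Average the two sessions at each time point, as the primary outcome already does, leaving four time points.
2. Prespecify an unstructured covariance with Kenward-Roger degrees of freedom, replacing both the AIC selection and the random-subject-effect version.
3. Name a fallback for non-convergence, for example a structure based on actual time between assessments.
4. State whether the reported 6-month interval is computed from observed changes or from the model.

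The planned separate fit by arm is a different question, and this change does not depend on it.

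The cost is wording only. Statistically, the model spends 4 × 5/2 = 10 covariance parameters instead of 2, a small loss of efficiency if compound symmetry holds. In the first-row scenarios, unstructured on the four averaged time points covered 94-95%.
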